12.6. Recording Adverse Events

Adverse events spontaneously reported by the subject and/or in response to an open question from the study personnel or revealed by observation will be recorded during the study at the investigational site. Clinically insignificant changes in laboratory values, BP, and pulse need not be reported as AEs. However, abnormal values that constitute an SAE or lead to discontinuation of administration of study drug must be reported and recorded as an AE. Information about AEs will be collected from signing of the consent form until the end of the study. Serious Adverse Event information will be collected from signing of the informed consent until 30 days following the last dose of study drug and for related SAEs, until resolution. The AE term should be reported in standard medical terminology when possible. For each AE, the Investigator will evaluate and report the onset (date and time), resolution (date and time), intensity, causality, action taken, serious outcome (if applicable), and whether or not it caused the subject to discontinue the study.

Intensity will be assessed according to the CTCAE v5.0 or [Section 12.4.4](#).

Should a pregnancy occur, it must be reported and recorded on the Sponsor's pregnancy form. Pregnancy in itself is not regarded as an AE unless there is a suspicion that a study drug may have interfered with the effectiveness of a contraceptive medication. Study IMP will stop immediately for female subjects who become pregnant.

The outcome of all pregnancies (spontaneous miscarriage, elective termination, normal birth, or congenital abnormality) will be followed up (assuming consent) and documented even if the subject was discontinued from the study.

All reports of congenital abnormalities/birth defects are SAEs. Spontaneous miscarriages should also be reported and handled as SAEs. Elective abortions without complications should not be handled as AEs.

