12.7. Reporting Adverse Events

All AE and SAEs (related and unrelated) will be recorded from the signing of consent form until the end of the safety reporting period (or until screen failure, 30 days following the end of treatment exposure or initiation of an investigational agent or cytotoxic chemotherapy, whichever occurs first). Any SAEs considered possibly or probably related to the study drug and discovered by the Investigator at any time after the study should be reported. All SAEs must be

reported to the Sponsor within 24 hours of the first Investigator awareness of the event. The Investigator must complete, sign and date the SAE pages, verify the accuracy of the information recorded on the SAE pages with the corresponding source documents, and send a copy to the Sponsor.

Additional follow-up information, if required or available, should all be reported to the Sponsor. Epizyme, Inc. following the same reporting timeline as the initial report, and this should be completed on a follow-up SAE form and placed with the original SAE information and kept with the appropriate section of the eCRF and/or study file.

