6.2.6. PARTIAL/MISSING DATES

For partial dates, the algorithms for imputation will vary depending upon the parameter; missing or incomplete medications start and stop dates will be imputed to determine whether the medications are taken prior to the study drug or concomitantly. Missing adverse event (AE) start dates will be imputed to determine whether the AEs are treatment emergent. In listings, all dates will be listed as recorded. The details of imputation algorithm rules can be found in [Appendix 1](#).

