16.1. ADVERSE EVENTS

AEs will be coded using MedDRA v23.1. Summary tables will be based on treatment emergent adverse events (TEAEs) which are defined as AEs that started or worsened in severity on or after the day of the first dose of study drug through 30 days after the end of study drug or the initiation of subsequent anticancer therapy, whichever is earlier. All AEs, treatment emergent or otherwise, will be presented in AE listings.

Each summary table will include the incidence (number and percentage) of subjects reporting any TEAE, as well as, by SOC and PT. A subject will be counted only once with an SOC, even if the subject experienced more than one TEAEs within that specific SOC (likewise for PT).

Investigator assessed severity grade will be based on the National Cancer Institute CTCAE v5.0. A subject will be counted only once with the worst severity grade within a SOC and/or PT.

Investigator assessed causality to study drug will be categorized as “not related,” “unlikely related,” “possibly related,” or “probably related” to study drug. For summary purposes, treatment-related TEAEs will include events with relationship to study drug classified as “not related” including both “not related” and “unlikely related” or “related” involving both “possibly related” and “probably related”. A TEAE with a missing causality will be classified as “related” to study drug. A subject will be counted only once at the strongest causality within a SOC and/or PT (related over not related).

TEAEs of special interest are defined in Section 12.4.2 of the protocol.

In accordance with the TEAE table presentation described above, AEs will be summarized as follows:

- TEAEs
- TEAEs of grade 3 or 4
- Treatment-related TEAEs
- Treatment-related TEAEs of grade 3 or 4
- TEAEs leading to dose interruption
- TEAEs leading to dose reduction
- TEAEs leading to discontinuation of study drug
- Serious adverse events (SAEs)
- Treatment-related SAEs

-
- TEAEs leading to death
 - TEAEs of special interest

For treatment-related summaries, relationship will be summarized by each study drug (Part 1: tazemetostat or itraconazole; Part 2: tazemetostat or rifampin).

Separate listings of SAEs, TEAEs leading to discontinuation of study drug, TEAEs leading to dose modifications, and TEAEs with an outcome of death will be provided. A listing of TEAEs of special interest will also be provided.

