18. REFERENCES

APPENDIX 1. PARTIAL AND MISSING DATES CONVENTIONS**ALGORITHM FOR TREATMENT EMERGENCE OF ADVERSE EVENTS****Table 2. Treatment-emergent Adverse Events**

START DATE	STOP DATE	ACTION
Known	Known/Partial/Missing	If start date < study drug start date, then not TEAE If start date >= study drug start date and < (end of treatment + 30 days) or start date of new anticancer therapy, whichever is sooner, then TEAE If start date > (end of treatment + 30 days) or start date of new anticancer therapy, whichever is sooner, then not TEAE
Partial, but known components show that it cannot be on or after study drug start date	Known/Partial/Missing	Not TEAE
Partial, could be on or after study drug start date	Known	If stop date < study drug start date, then not TEAE If stop date >= study drug start date, then TEAE
	Partial	Impute stop date as latest possible date (i.e. last day of month if day unknown or 31st December if day and month are unknown), then: If stop date < study drug start date, then not TEAE If stop date >= study drug start date, then TEAE
	Missing	Assumed TEAE
Missing	Known	If stop date < study drug start date, then not TEAE If stop date >= study drug start date, then TEAE
	Partial	Impute stop date as latest possible date (i.e. last day of month if day unknown or 31st December if day and month are unknown), then: If stop date < study drug start date, then not TEAE If stop date >= study drug start date, then TEAE
	Missing	Assumed TEAE

ALGORITHM FOR PRIOR AND CONCOMITANT MEDICATIONS**Table 3. Prior and Concomitant medications**

START DATE	STOP DATE	ACTION
Known	Known	
If stop date < study drug start date, assign as prior.
 
If stop date >= study drug start date & start date<=end of study treatment or discontinued date of study drug, assign as concomitant.
 
If stop date>=study drug start date & start date < study drug start date, assign as both prior and concomitant.

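### SAP Appendix 1, Table 2 does not test partial AE start dates against the end of the TEAE window, so an onset month or year wholly after the cutoff is still classed as treatment-emergent

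*SAP*

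**What the plan says.** SAP 16.1 defines TEAEs as events that start or worsen from the day of first dose "through 30 days after the end of study drug or the initiation of subsequent anticancer therapy, whichever is earlier". SAP 6.2.6 says that "Missing adverse event (AE) start dates will be imputed to determine whether the AEs are treatment emergent" and refers to Appendix 1 for the rules. SAP 7 also names Appendix 1 as the rule for incomplete AE dates.

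In Appendix 1, Table 2, the known-start row applies both ends of the window. Its upper end reads "If start date > (end of treatment + 30 days) or start date of new anticancer therapy, whichever is sooner, then not TEAE".

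Partial start dates are divided into two groups:

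- The first is "Partial, but known components show that it cannot be on or after study drug start date". These events are not TEAEs.
- The second is "Partial, could be on or after study drug start date", which takes every other partial date. With a known stop date, or a partial one imputed to its latest possible date, the action is "If stop date >= study drug start date, then TEAE"; a stop before first dose is not a TEAE. With a missing stop date, the event is assumed to be a TEAE.

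Fully missing start dates follow the same stop-date tests. No partial-start or missing-start row mentions the end of treatment, the 30 days, or new anticancer therapy.

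**The concern.** Table 2 uses the known part of a date to exclude events that must have begun before first dose, but does not use it to exclude events that must have begun after the window closed. Two events with onset in the same month, both after the cutoff, are then classified differently only because one has a recorded day. The classification depends on how complete the date is, not on when the event began.

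The TEAE flag underlies the adverse event summaries in SAP 16.1, including the treatment-related and special-interest tables. With small numbers per part, a single late event that began under another anticancer therapy can be visible in a sparse row.

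**Working it through.** **1. The rules side by side**

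| Recorded start | Test against first dose | Test against cutoff |
|---|---|---|
| Known | Yes | Yes |
| Partial, known part entirely before first dose | Yes | Not needed |
| Partial, any other | Through the stop date only | None |
| Missing | Through the stop date only | None |

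The cutoff is the sooner of (end of treatment + 30 days) and the start of new anticancer therapy.

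**2. Example with the 30-day cutoff (invented dates)**

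First dose 10 Jan 2022, last dose 17 Feb 2022, no new therapy. Cutoff = 17 Feb + 30 days = 19 Mar 2022. Table 2 was coded as written and run:

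| Start | Stop | Table 2 result | Known-start row, first and last day of that month |
|---|---|---|---|
| Mar 2022, day unknown | 1 Jun 2022 or missing | TEAE | TEAE / not TEAE |
| Apr 2022, day unknown | 1 Jun 2022 or missing | TEAE | not TEAE / not TEAE |
| May 2022, day unknown | 1 Jun 2022 or missing | TEAE | not TEAE / not TEAE |

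March contains the cutoff, so onset inside the window cannot be ruled out and TEAE is a sound default. April and May lie wholly after it. There Table 2 contradicts both its own known-start row and SAP 16.1.

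**3. Example with new therapy (invented dates)**

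Last dose 10 Mar, new anticancer therapy 25 Mar, AE start April with day unknown, stop 20 Apr. The 30-day limit is 9 Apr, so the cutoff is 25 Mar. Every April day is after it, yet Table 2 returns TEAE. A known start of 1 Apr returns not TEAE. Without the new therapy the cutoff would be 9 Apr, April would contain in-window days, and there would be no conflict.

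**4. Can such records exist?**

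- Protocol 12.7 and footnote m of the protocol's Tables 3 and 4 end AE collection at 30 days after treatment, or at an investigational agent or cytotoxic chemotherapy if sooner. The SAP window ends at any subsequent anticancer therapy. If the new therapy is neither investigational nor cytotoxic, the SAP window closes while collection continues. In step 3 that gap runs from 25 Mar to 9 Apr.
- Protocol 12.7 says that possibly or probably related SAEs "discovered by the Investigator at any time after the study should be reported". These fall after the window if they are entered in the database, which the text does not state.
- Protocol 12.6 says "Information about AEs will be collected from signing of the consent form until the end of the study", and the end-of-study visit is allowed at 30 (±3) days, so up to day 33. A conflict by this route would need the cutoff at a month end and an unknown onset day within the next three days.

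**5. Size**

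Protocol 7.2 and SAP 4.2 plan about 40 subjects, to give 12 completers per part with about 40% drop-out. 12 / (1 − 0.40) = 20 per part, which agrees with 40 split equally. If all 20 are dosed, one subject is 1/20 = 5.0 percentage points in a part-level row, and 1/40 = 2.5 points in the overall column.

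**6. After the change**

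With one added test (earliest possible start after the cutoff: not TEAE), the April and May rows in step 2 become not TEAE whether the stop date is known or missing. March stays TEAE.

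**The case against.** The strongest defence is that counting uncertain events as treatment-emergent is the usual conservative choice in safety reporting. That holds where onset inside the window is possible. A reader might infer that all the partial-start and missing-start rows are wrong because none tests the cutoff; the documents do not support this. For a fully missing start, or a partial date that includes in-window days, onset in the window cannot be excluded. The defence fails only where the recorded month or year already excludes it. The medication algorithm in Appendix 1, Table 3 imputes a partial start to its earliest possible date and tests it against the end of treatment, so using the known components at the upper end is not foreign to this SAP.

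A second objection is that such records will be rare. This stands. Protocol 12.6 read alone suggests collection with no stop at new therapy, but 12.7 and the schedule footnotes narrow it, and 12.6 also asks for the date and time of onset of each AE. Nothing in the documents shows that late SAEs are more likely to have partial dates.

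A third is that the error only over-includes, in descriptive secondary safety tables. All AEs are listed whether or not treatment-emergent, with dates as recorded, and the PK endpoints are untouched. This stands too, and keeps the point minor.

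**Conclusion.** The point holds in a narrow form. A partial start whose known month or year lies wholly after the cutoff is classed as TEAE by Table 2, against SAP 16.1 and Table 2's own known-start row. SAP 6.2.6 and SAP 7 do not correct this, because both send the reader to Appendix 1.

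The effect is small: probably few events, each moving a part-level row by at most about 5 points. This assumes about 20 dosed per part. It also requires that the subject has no other qualifying event in the row, since SAP 16.1 counts each subject once per SOC or PT. In the any-TEAE row the effect is likely nil: Protocol 5.5.1 reports at least one TEAE in 857 of 895 (96%) subjects on monotherapy.

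A reader might infer a shift of 1/12 = 8.3 points for every misclassified subject. That uses the completer target. The Safety population in SAP 5 is built on dosed subjects, so the expected denominator is nearer 20, and even then the figure is an upper bound.

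**What to change.** Add one row to SAP Appendix 1, Table 2, ahead of the row for partial dates that could be on or after first dose:

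- Start date: partial, where the known components place the earliest possible start later than the sooner of (end of treatment + 30 days) and the start of new anticancer therapy.
- Stop date: known, partial or missing.
- Action: not TEAE.

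Leave every other partial-start and missing-start row unchanged, including the stop-date tests. In particular, do not shorten the missing-start rows to a blanket assumption of TEAE: they correctly exclude an event whose stop date precedes first dose, and only a missing start with a missing stop is assumed to be a TEAE.

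The cost is one row in the SAP and one condition in the derivation program, made before database lock. No new data are needed.

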13.2. PRIOR AND CONCOMITANT MEDICATIONS

Medications will be summarized and listed for the Safety population. Summary tables will include incidence (number and percentage) of subjects receiving any medication and incidence of specific medications by WHO Drug ATC level 4 and PT.

Prior and concomitant medications will be summarized separately. Categorization will be defined as follows:

- Prior medications will include medications which stopped prior to the first dose of study drug.
- Concomitant medications are defined as medications that were started at any time after the start of first dose of study drug and stopped prior to the end of study treatment or the discontinuation of study drug, whichever is earlier.
- Medications that started prior to the first dose of study drug and continued into study treatment period until the end of study treatment or the discontinuation of study drug, whichever is earlier, are considered as both prior and concomitant.
- Post-treatment medications will include anticancer therapies which started after discontinuation of study drug.

Medications with missing or partially missing start or end dates will be handled according to the conventions described in Appendix 1. If it cannot be determined whether a medication was a prior medication due to partial medication start date or end date, the medication will be considered concomitant. If medication start date and end date are missing, the medication will be considered concomitant. Prohibited medications, as defined in Section 9.3 of the protocol, will be identified with a '*' in the listing.

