	Partial	
Impute stop date as latest possible date (i.e. last day of month if day unknown or 31st December if day and month are unknown), then:
 
If stop date < study drug start date, assign as prior.
 
If stop date >= study drug start date & start date<=end of study treatment or discontinued date of study drug, assign as concomitant.
 
If stop date>=study drug start date & start date < study drug start date, assign as both prior and concomitant.

	Missing	
If stop date is missing could never be assumed a prior medication.
 
If start date <=end of study treatment or discontinued date of study drug, assign as concomitant.

Partial	Known	
Impute start date as earliest possible date (i.e. first day of month if day unknown or 1st January if day and month are unknown), then:
 
If stop date < study drug start date, assign as prior.
 
If stop date >= study drug start date & start date<=end of study treatment or discontinued date of study drug, assign as concomitant.
 
If stop date>=study drug start date & start date < study drug start date, assign as both prior and concomitant.

	Partial	
Impute start date as earliest possible date (i.e. first day of month if day unknown or 1st January if day and month are unknown) and impute stop date as latest possible date (i.e. last day of month if day unknown or 31st December if day and month are unknown), then:
 
If stop date < study drug start date, assign as prior.
 
If stop date >= study drug start date & start date<=end of study treatment or discontinued date of study drug, assign as concomitant.
 
If stop date>=study drug start date & start date < study drug start date, assign as both prior and concomitant.

	Missing	
Impute start date as earliest possible date (i.e. first day of month if day unknown or 1st January if day and month are unknown), then:
 
If stop date is missing could never be assumed a prior medication.
 
If start date <=end of study treatment or discontinued date of study drug, assign as concomitant.

Missing	Known	
If stop date < study drug start date, assign as prior.
 
If stop date >= study drug start date, assign as concomitant.

START DATE	STOP DATE	ACTION

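### SAP Appendix 1 Table 3 has no floor at the last dose, so a partially dated next-line anticancer therapy can be classed as concomitant; the SAP also gives no rule for a partial therapy date in the TEAE and end-of-treatment cutoffs

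*SAP*

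**What the plan says.** SAP 13.2 sends all partially dated medications to the appendix: "Medications with missing or partially missing start or end dates will be handled according to the conventions described in Appendix 1". The same section sets up a separate class: "Post-treatment medications will include anticancer therapies which started after discontinuation of study drug".

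All three partial-start rows of Appendix 1 Table 3 (stop date known, partial or missing) begin with the same step: "Impute start date as earliest possible date (i.e. first day of month if day unknown or 1st January if day and month are unknown". The imputed date then meets the test "start date<=end of study treatment or discontinued date of study drug, assign as concomitant". Where the stop date is known or partial, a further branch makes the drug prior and concomitant at once if the imputed start precedes first dose. Where the stop date is missing, the drug can never be prior. No visible row has a post-treatment outcome.

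SAP 6.2.6 gives the purpose of the imputation: "missing or incomplete medications start and stop dates will be imputed to determine whether the medications are taken prior to the study drug or concomitantly". SAP 16.1 runs the TEAE window "through 30 days after the end of study drug or the initiation of subsequent anticancer therapy, whichever is earlier". For AEs with a known start date, Table 2 applies the same limit: "If start date > (end of treatment + 30 days) or start date of new anticancer therapy, whichever is sooner, then not TEAE". SAP 6.2.4 ends its window for the end-of-treatment result in the same way. None of these three places says what to do when the therapy's own start date is partial.

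**The concern.** Two parts of the SAP disagree about the same record. SAP 13.2 puts a therapy begun after study drug in the post-treatment class. Table 3, to which SAP 13.2 refers partial dates, can move its start back before the last dose and call it concomitant. Concomitant medication monitoring is one of the safety parameters listed under the secondary objectives, and protocol 9.2.3 prohibits antineoplastic therapy on study. A subject who stopped study drug and then properly moved to a next line could thus be counted in the summary as having taken a prohibited drug during treatment.

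The second issue is an omission. Three rules depend on the start date of new anticancer therapy, and the only imputation the SAP states for a medication start is the earliest possible date. A programmer with a partial therapy date has to choose something. Taking over the Table 3 date could put the cutoff before the last dose.

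**Working it through.** The plan states no figure on this point, so there is none to reproduce. The documents give no subject dates; all dates below are illustrative. I take end of treatment in Table 3 to be the date of last dose.

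**Notation.** F = first dose, L = last dose, I = imputed start (first of the known month, or 1 January of the known year). Table 3 gives concomitant if I ≤ L and the stop date is missing or ≥ F. It gives prior and concomitant at once if also I < F and the stop date is known or partial.

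**Step 1: classification.** F = 10 January 2022, L = 20 March 2022. The stop date, if recorded, is after F.

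| Recorded start | True start | I | Table 3 result | I with floor at L + 1 |
|---|---|---|---|---|
| March 2022, day unknown | 28 March | 1 March | concomitant | 21 March |
| 2022 only, stop known or partial | 28 March | 1 January | prior and concomitant | 21 March |
| 2022 only, stop missing | 28 March | 1 January | concomitant | 21 March |
| April 2022, day unknown | 5 April | 1 April | no branch applies | 1 April |

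The first three rows are wrong against SAP 13.2. The fourth is not misclassified, but Table 3 gives it no category. The error needs the known month or year to be that of the last dose.

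**Step 2: how often, given a partial date.** With a 30-day month, last doses spread evenly and a true gap of g days, a day-unknown start falls in the month of last dose with probability (30 − g)/30:
- g = 7: 23/30 = 0.77
- g = 14: 16/30 = 0.53
- g = 21: 9/30 = 0.30

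As a check, I took every calendar date in 2021–2022 as a last dose and weighted all gaps equally:

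| Gaps covered | Day unknown: I ≤ L | Year only: I ≤ L |
|---|---|---|
| 1–14 days | 75.3% | 97.9% |
| 1–30 days | 49.1% | 95.8% |
| 1–60 days | 24.5% | 91.6% |

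**Step 3: the cutoff, only if the Table 3 date were reused (the SAP does not say so).** Window end = min(L + 30 days, I).
- Day unknown: the window ends 1 March. AEs with known starts on 2–20 March (19 on-drug days) become non-TEAEs. An AE on 1 March meets neither the earlier-than nor the later-than branch of Table 2.
- Year only: the window ends 1 January. All 22 + 28 + 20 = 70 treatment days fall after it.
- On average, for a misclassified day-unknown record: L is uniform on days 1 to 30 − g and L − 1 days are lost, so the mean is (29 − g)/2, which is 11.0, 7.5 and 4.0 on-drug days for gaps of 7, 14 and 21 days.

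Only AEs with a known start date are exposed, because the partial and missing AE-start rows of Table 2 have no upper limit.

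**Step 4: the cutoff with the floor.** In the March example the window ends 21 March. No on-drug day is lost. The true date would have ended it on 28 March, so 7 post-treatment days go. When the floor determines the date, the loss is g − 1 days, so 13 for a 14-day gap.

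**The case against.** The strongest objection concerns the TEAE window. A reader might infer that Table 3 closes it while the subject is still on drug. The documents do not support that. SAP 6.2.6 limits medication-date imputation to prior versus concomitant status; Table 2, SAP 16.1 and SAP 6.2.4 do not import the imputed date; and their words (new, subsequent) imply a therapy that follows study drug. This objection stands: what remains is a missing rule, not a wrong one.

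A reader might also infer false protocol deviations. SAP 10 does not derive deviations from Table 3, the asterisk in the SAP 13.2 listing marks drugs that the protocol prohibits and not a Table 3 label, and listings show dates as recorded. That too stands; the misleading entry is in the summary.

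A third defence is that leaning towards concomitant is policy: "due to partial medication start date or end date, the medication will be considered concomitant". That fallback covers only doubt about whether a drug was prior. It does not settle concomitant against post-treatment, so it does not answer the point.

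Two limits also hold. The protocol ends AE reporting, and brings the safety visit forward, when an investigational agent or cytotoxic chemotherapy starts, so sites have reason to establish those dates. And the last missing-start rows of Table 3 are not in the text available to me, so the absence of a post-treatment outcome is confirmed only for the visible rows. The partial-start rows are complete.

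**Conclusion.** The classification fault holds as written in the SAP. A subsequent anticancer therapy is labelled concomitant when its known month (or, for a year-only date, its known year) is that of the last dose. It is labelled prior as well when only the year is known, that year is also the year of first dose, Day 1 is later than 1 January, and a stop date is known or partial. Given a day-unknown date, the risk is roughly 30% to 77% for gaps of 21 down to 7 days; for year-only dates it is above 90% over the gaps examined. These shares rest on evenly spread last doses and on end of treatment being the last dose date.

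The handling of partial therapy dates in Table 2, SAP 16.1 and SAP 6.2.4 is unspecified. Loss of on-drug AEs would follow only if the Table 3 date were reused, which the SAP does not state.

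The number of partial dates is unknown, and only descriptive safety tables are touched; the PK objectives are not. It merits correction before database lock because a stated rule gives a wrong result and the remedy is short.

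**What to change.** Add to Appendix 1, in words such as:

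> For an anticancer therapy recorded as subsequent to study drug, a partial start date is set to the later of the earliest possible date and the day after the last dose, unless the known components place it earlier. Such a therapy is a post-treatment medication. The same date is used for the cutoffs in Table 2, Section 16.1 and Section 6.2.4.

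Table 3 needs a post-treatment outcome, tested before the concomitant one. Table 3 compares with the end of treatment or the discontinuation date and does not say that this is the last dose. If the recorded date is later than the last dose, the day after last dose would still pass the concomitant test.

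The rule assumes that the eCRF identifies a therapy as subsequent; the documents supplied do not show that form.

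Cost: a few sentences in the SAP and a few lines of derivation code before lock. Downside: the floored date can end the post-treatment part of the TEAE window up to g − 1 days before the true therapy start, but it removes no on-drug day.
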